desired behaviors such as retention. CM, however, has not yet been tested or adapted for use in community-based programs for offender populations, particularly to encourage treatment admission and attendance.

The study will provide incentives to study participants for enrollment at the Walden House program and for attendance during the residential and the outpatient phases at Walden House. For a continuum of care model (such as that provided by CDCR), enrolling in community treatment is essential and increases the likelihood that clients will receive the benefits of treatment. In addition, increasing the amount of time that clients participate in residential and outpatient treatment is an important goal for improving outcomes. Only about 56% of clients referred from the SATF prison treatment programs to Walden House show up for admission, and the average length of attendance is 38 days. Increased enrollment would mean that a larger percentage of participants from prison-based treatment would be exposed to continuing treatment in the community, thereby improving the overall efficiency of CDCR's treatment system. Increased attendance would mean that clients have greater exposure to the treatment environment and treatment activities of the Walden House program, with the likelihood that this would improve post-treatment outcomes.

INTRODUCTION TO THE STUDY

The UCLA Integrated Substance Abuse Programs (ISAP), in collaboration with Walden House and the California Department of Corrections and Rehabilitation, is conducting a five-year health services research study that will involve a randomized test of the use of incentives to improve treatment utilization among parolees in community-based treatment. The incentives are in the form of vouchers that are redeemable for cash deposited into their Walden House bank account. The goals of the study are to increase the likelihood that prison treatment participants with a referral to community treatment will actually enroll in community treatment following release to parole and, once enrolled, will increase the amount of time that they participate in treatment. Increased exposure to community treatment as a result of incentives is expected to result in improved long-term outcomes of parolees who have participated in prison-based and community-based treatment.

The study has six specific aims:

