Data Entry, Quality Control, and Data Security. Items on the instruments are close-ended with predetermined response categories. The interviewer edits responses for completeness, consistency, and legibility. Several options are available to data capture. ISAP's Data Management Center (DMC) has extensive experience in creating forms that are faxed to ISAP and scanned into a computerized format. Use of faxed forms allows for virtually instantaneous

data entry with a minimum of error. As an alternative to faxable TeleForms, the DMC has the capability to use PDF+ Forms, which create standard PDF files that can be used within Adobe Acrobat Reader and other PDF applications. These forms can then be distributed, filled out, and collected via email, paper hard copy, or posted on the Web. In addition to being identical to the TeleForms paper forms, the PDF+ forms have field-level checks and drop-down boxes for easier data entry. However we decide to capture the interview data, the interview responses are automatically checked against pre-set standards. Errors are flagged and resolved by the data entry clerk, the interview editor, or the original interviewer. Completed instruments are stored in locked files in a room with an off-master key. Access is limited to individuals who have a research need for the data and who have signed confidentiality statements. The master list linking subject names to code numbers is stored on a password-protected computer. The DMC maintains the security of data by storing data on a secure server, conducting regular backups onto separate media, and storing backup media off-site (see ISAP's data security policies in Appendix C).

DATA ANALYSIS PLAN

PRIMARY AIMS

Primary analyses for the study will be directed toward testing hypotheses (H) and answering research questions (RQ) associated with the study's specific aims.

Aim 1 Determine whether offering an incentive (voucher) increases admission to community treatment by parolees who have participated in prison treatment.

H1. Participants in the Admission Incentive group will be more likely to show up for admission to the Walden House program than will participants in the Admission Information group.

H2. Of participants who are admitted to the Walden House program, those in the Admission Incentive voucher group will have a shorter time to admission than those in the Admission Information group.

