RQ2. Were treatment staff members able to adhere to the procedures of the Contingency Management Manual?

RQ3. Were there programmatic, logistic, or other issues that facilitated or compromised the implementation of the intervention?

RQ4. What factors are likely to promote or impede the sustainability of the CM intervention beyond the end of the study?

QUANTITATIVE ANALYSES

Overview. Consideration of specific aims, hypotheses, data structures, and available resources will determine the choice of analytic approaches. Analyses will examine both significant differences (if any) between the groups on the outcomes of interest and the magnitude of the difference (i.e., effect size). The main analyses will follow the “intent-to-treat” approach in which we will include all clients in the analysis for whom data are available, whether they have completed treatment or not (Nich & Carroll, 2002). Methods that provide unbiased effects in the face of non-compliance (e.g., Complier Average Causal Effect analysis) may also be used. The following discussion covers power analysis, preliminary and descriptive analyses, design analyses, hypothesis testing, and other analyses.

POWER ANALYSIS

The study is powered for the two primary aims: whether incentives increase admission and whether they increase attendance. Two meta-analyses of contingency management have found that the average effect size for outcomes measured during or at the end of treatment is in the medium range (using Cohen’s guidelines; Cohen, 1988). Lussier et al. (2006) reported an average effect size (using a random effects model) for abstinence outcomes of $d = 0.67$ (transformed from $r = 0.32$). Prendergast et al. (2006), using a partially overlapping but larger set of studies, found an effect size (random effects) for drug use outcomes (not necessarily abstinence) of $d = 0.49$. A recent study (Alessi, Hanson, Wieners, & Petry, 2007) examined the effects of CM (using prize-based incentives) on group therapy attendance over 12 weeks, reporting an effect size of $r = .17$ ($d = 0.34$). CM studies have not examined the effect of incentives on enrollment in treatment or on attendance over longer periods of time (e.g., 26

weeks), but it is reasonable to assume that effect sizes for these outcomes would also be in the low medium range.

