For the primary outcomes of admission and attendance, there will be no attrition since these outcomes will be based on program records. For the Admission Phase, the target sample size of 250 will allow detection of medium effects in comparisons between groups on the percentage of clients who enroll in treatment at Walden House, with $\alpha = .05$ (two-tailed) and power .80. For the Attendance Phase, with retention as the outcome, the sample size of 200 will allow detection of similar effects between groups. For the 12-month outcomes, the effect size will be smaller, possibly around $d = 0.30$, based on a previous meta-analysis of drug abuse treatment generally (Prendergast, Podus, Chang, & Urada, 2002). Here, where the analysis will be based on the follow-up interview sample in the Attendance Phase (~170), power is likely to be about .75. For arrest and reincarceration, where there will be no attrition, power will be at least .80. Inclusion of covariates may increase power somewhat (Tabachnick & Fidell, 1996).

PRELIMINARY AND DESCRIPTIVE ANALYSES

As noted above, faxable forms will allow many of the instruments to be quickly entered and checked, making it possible to periodically examine the data. Descriptive statistics on variables of interest will include percentages, means, correlations, measures of variance, and distribution characteristics, as appropriate to the measurement level of selected variables. Frequency tables will be used to examine cell sizes for categorical variables and non-normality for continuous variables. Where categorical variables have small cell sizes, we will collapse the categories where possible to create cells of sufficient size. Where variables are non-normally distributed, we will transform the variable if possible or use a non-parametric approach. If outliers are present, they may be recoded or omitted. Descriptive analyses will provide statistics on treatment-related variables, including percentage of sessions attended, number of weeks attended, value of vouchers earned, and items for which vouchers were redeemed.

DESIGN ANALYSES

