Although the validity of self-report by clients of their behavior is often in question, prior research indicates that self-report interviews, when properly conducted, are generally reliable and valid in measuring drug and alcohol use (Buchan, Dennis, Tims, & Diamond, 2002; Chou, Hser, & Anglin, 1996; Darke, 1998) and criminal involvement (Elliot, Huizinga, & Ageton, 1982; Junger-Tas & Marshall, 1999; Thornberry & Krohn, 2000). Biological-based data increases the credibility of findings from self-report, but such data cannot reveal distant use or long-term patterns of use, nor can criminal justice records verify criminal behavior that does not come to official attention. Still, policy makers prefer objective measures of criminal justice involvement to self-reported measures. For the proposed study, we will use several procedures to increase the reliability and validity of self-report data. First, interviewers will assure participants that information that they provide as part of research will not be revealed to parole or other agencies, will not become part of their parole or treatment records, and is protected by a certificate of confidentiality. Second, interviewers will inform participants at the start of the follow-up interview that they will be asked to provide a urine specimen after the interview that will be tested for illicit drugs. Third, with respect to criminal justice system involvement, we will obtain official arrest and incarceration records from the California Department of Justice and the California Department of Corrections and Rehabilitation, which can be used to verify self-reported arrest and incarceration.

HYPOTHESIS TESTING

For the Admission Phase, the independent variables are Admission Incentive vs. Admission Comparison. For the Attendance Phase, the independent variables are Attendance Incentive vs. Attendance Comparison.

Primary dependent variables will be the proximal outcomes of treatment admission and retention. Secondary dependent variables will be the distal outcomes of substance use, crime, and psychosocial functioning, including employment, education, family relationships, psychological functioning, and HIV risk.

Treatment admission. Whether study participants completed intake for admission to the Walden House residential program and the outpatient program will be based data from program records. Time to admission, calculated from date of parole release to date of enrollment, will also be examined.

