Hypothesis tests are based on the assumption of group equivalence due to random assignment. However, if preliminary analysis indicates significant baseline differences, then additional control variables will be included in the analyses. Hypotheses will be tested using a two-sided .05 level of significance.

Hypotheses will initially be tested using t-tests and chi-square tests. T-tests will be used to conduct pairwise comparisons of participants in the study groups on outcomes measured as a single continuous variable. For categorical and binary outcome variables, we will use chi-square analysis. If covariates are required, analyses will be extended to ordinary least squares (OLS) or logistic regression as appropriate to the scale properties of the dependent variable. Because of missing data, inclusion of covariates, and/or repeated measures for binary outcomes, analyses may be extended to generalized linear models (McCullagh & Nelder, 1989). Structural equation modeling will be used to determine whether the effect of incentives on distal outcomes is mediated by program admission, treatment activities, admission, or retention (Kaplan, 2000).

For each hypothesis, an effect size will be calculated. The index of effect size will be the standardized mean difference (calculated as the difference between two groups divided by the pooled standard deviation); for proportions, the equivalent effect size is calculated using the arc sine transformation (Lipsey & Wilson, 2001). An effect size for study outcomes will provide a

quantitative indication of the magnitude of the difference between groups; it will also be useful in calculating power for any future study of this intervention.

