The main approach to estimating treatment effects will be an intent-to-treat (ITT) analysis. This approach provides an unbiased estimate of the causal effect of random assignment (or the offer of treatment). But since there may be noncompliance and crossover from one group to another (despite the best efforts of the researchers to prevent it), the ITT approach does not provide an estimate of the causal effect of receipt of treatment, which is what treatment providers and policy makers are mainly interested in. If compliance is a problem, we will supplement ITT with an analysis that provides an estimate of the more clinically relevant Complier Average Causal Effect (CACE) (Dunn, Maracy, & Tomenson, 2005; Little & Yau, 1998). According to CACE methodology, owing to randomization, the proportion of compliers in the control group (an unobserved latent class) is, on average, the same as the proportion of compliers in the treatment group. The CACE represents a difference of outcomes between these two groups that is an unbiased estimate of the treatment effect among compliers.

OTHER ANALYSES

Additional analyses, while not testing specific hypotheses, will address related topics of interest, including, for example, responsiveness to the CM intervention by risk level and Anti-Social Personality Disorder, influence of motivation on outcomes, impulsiveness, time to dropout or rearrest, and predictors of levels of participation. OLS will be used to assess the association of participant characteristics with continuous dependent variables, and logistic regression will be used to assess the association of characteristics with binary variables. For date-based outcomes, Cox proportional hazards regression (Hosmer & Lemeshow, 1999) will be used to analyze elapsed time to a particular event (e.g., time to treatment enrollment or dropout, time to rearrest). This technique allows for the inclusion of covariates to control for any measured baseline differences between the groups. Although cell sizes may be too small to support strong conclusions about differential outcomes by subgroups (e.g., race/ethnicity, primary drug), subgroup findings may suggest either refinements in the protocol or hypotheses to be considered in future studies.

QUALITATIVE ANALYSES

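### H2 compares time to admission only among those admitted, a subset the voucher is meant to change, so the comparison is not randomized and its bias has unknown direction

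*Protocol*

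**What the plan says.** All references are to the Protocol.

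- **Primary Aims, Aim 1.** H1 states: "Participants in the Admission Incentive group will be more likely to show up for admission to the Walden House program". H2 then narrows the population: "Of participants who are admitted to the Walden House program, those in the Admission Incentive voucher group will have a shorter time to admission". The comparator is the Information group.
- **Hypothesis Testing, treatment admission.** "Time to admission, calculated from date of parole release to date of enrollment, will also be examined". The variable therefore has a value only for people who enroll.
- **Hypothesis Testing, general rule.** Tests rest on the groups being equivalent through random assignment, at a two-sided .05 level. For continuous outcomes, "T-tests will be used to conduct pairwise comparisons of participants in the study groups on outcomes measured as a single continuous variable". No test is assigned to H2 by name.
- **Other Analyses.** Cox regression is named for date-based outcomes, with the examples "time to treatment enrollment or dropout, time to rearrest". The section introduces its contents as not testing specific hypotheses.
- **Reinforcement Schedule, Admission Phase.** The admission voucher is paid only to those who show up within two weeks of release.
- **Power Analysis.** "the target sample size of 250 will allow detection of medium effects in comparisons between groups". The outcome meant is the share enrolled, and power is .80. No figure is given for H2. The section also says there is no attrition for admission, because it comes from program records.

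**The concern.** H2 conditions on an event that occurs after randomization and that the trial expects to differ by arm. If H1 is false, the admitted groups remain comparable. If H1 is true, they do not: the admitted Incentive group is a mixture of people who would have come anyway and people who came only for the voucher, while the admitted Information group holds only the first kind. A difference in mean days then combines any real speed-up with a difference in who is being averaged.

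At stake is the interpretation of one of the two hypotheses under Aim 1. A voucher that brings people in and speeds others up could show a longer mean time to admission. A voucher that speeds nobody up could show a shorter one. The people who never enroll, whose status is fully known from program records, are left out by definition.

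**Working it through.** **Inputs from the Protocol.** Control admission rate pC = 0.56, from the section on the problem addressed ("Only about 56% of clients referred from the SATF prison treatment programs to Walden House show up for admission"). N = 250, randomized 1:1, so 125 per arm; two-sided alpha .05; power .80.

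**Step 1: the plan's own figure.** The effect detectable with 125 per arm is h = (1.960 + 0.842) × √(2/125) = 0.354. Power at h = 0.354 is 0.799, and at the conventional medium value of 0.50 it is 0.977. So N = 250 is consistent with medium effects at power of at least .80, although no numeric effect is stated from which exactly 250 follows. For enrollment and attendance the plan expects that "it is reasonable to assume that effect sizes for these outcomes would also be in the low medium range"; at h = 0.34 power is 0.767.

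**Step 2: what this implies for who is admitted.** On the arcsine scale, h = 0.354 from 56% gives pI = 0.728; h = 0.50 gives pI = 0.791. Assume the voucher deters nobody who would otherwise have come.

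- Admitted: 125 × 0.56 = 70 Information and 125 × 0.728 = 91 Incentive. H2 leaves out 250 − 161 = 89 people.
- Share of admitted Incentive participants present only because of the voucher: 1 − 0.56/0.728 = 23% (29% at h = 0.50).

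**Step 3: the bias in closed form.** Let m be the mean days of admitted controls, δ the true speed-up among those who would come anyway, and M the mean days of voucher-induced entrants. Then

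Incentive − Information = [pC(m − δ) + (pI − pC)M]/pI − m = [(pI − pC)(M − m) − pC·δ]/pI.

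This is positive, so the sign is wrong, when M − m > δ × pC/(pI − pC). The multiplier is 0.56/0.168 = 3.3 (2.4 at h = 0.50).

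**Step 4: illustrations.** The Protocol gives no admission times, so every time here is an assumption: m = 4 days, gamma-distributed times, pI = 0.728, 4,000 simulated trials. The last two columns are a log-rank analysis of all 250 with the non-admitted censored at day 60 (also assumed); a hazard ratio above 1 means faster admission with the incentive.

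| δ | M | Admitted-only difference (days) | t-test among the admitted | All-randomized HR | Significantly faster |
|---|---|---|---|---|---|
| 1 | 4 | −0.77 | shorter, significant in 50% | 1.66 | 89% |
| 1 | 8 | +0.16 | wrong sign in about 60% | 1.54 | 77% |
| 1 | 10 | +0.62 | wrong sign in 87% | 1.49 | 73% |
| 0 | 10 | +1.39 | longer, significant in 66% | 1.39 | 55% |
| 0 | 4 | 0.00 | each direction about 2.6% | 1.51 | 74% |
| 0 | 2 | −0.46 | shorter, significant in 20% | 1.62 | 86% |

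Check of the third row: (0.168 × 6 − 0.56 × 1)/0.728 = +0.62. Check of the last: (0.168 × (−2))/0.728 = −0.46.

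The third row shows a true one-day speed-up appearing as a delay. The last shows an apparent speed-up with nobody sped up. The fifth shows the limit of the alternative: with no speed-up and induced entrants as prompt as the others, the all-randomized test is still significant in 74% of trials, because more people are admitted.

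**The case against.** **The direction of bias is not known.** A reader might infer that the bias runs toward apparent delay, because hesitant clients come late. Nothing in the Protocol says so. The two-week voucher deadline could make induced entrants early, which would favor H2. Reversal also needs a lag of more than about three times the speed-up. This objection stands: only an unknown direction can be claimed.

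**The conflict with intention-to-treat is weaker than it looks.** A reader might infer that H2 breaches the plan's ITT and analyze-as-assigned commitments. The Quantitative Analyses overview defines ITT as covering clients with available data, and the Randomization section raises analysis as assigned in connection with crossovers. H2 still compares arms as assigned and states its restriction openly. The firmer ground is the equivalence assumption under Hypothesis Testing, which the admitted subset does not keep if H1 is true.

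**The test is inferred and Cox is already named.** No test is fixed for H2, and an SAP could choose one. But the restriction to the admitted is in the hypothesis itself, and a different test on that subset does not remove the selection. Cox regression is placed among analyses that do not test hypotheses, and nothing says it replaces H2 or includes the non-admitted as censored. The baseline equivalency check is planned by phase, not within the admitted subset.

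**The alternative asks a different question.** With about 44% of controls never admitted, an all-randomized test is driven largely by the admission proportion. This is correct and has to be stated with the result.

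**The consequence is limited.** The study is powered for admission and attendance; time to admission is additional. This also stands.

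**Conclusion.** The point holds in a limited form. H2 as worded is a non-randomized comparison whenever H1 is true, and no other part of the Protocol cures this. The share of admitted Incentive participants present only because of the voucher, 23% at 56% against 72.8%, rests on the historical show-up rate, on the effect detectable at N = 250, and on the voucher deterring nobody. The 3.3-fold reversal threshold follows from the same inputs. The differences in days rest on assumed times and show only what is possible.

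It would go too far to say that H2 will come out reversed or that it is biased toward delay. If the voucher does not change admission, the selection disappears. H1, which uses everyone randomized, and the sample size of 250 are untouched. The point merits a correction to a numbered Aim 1 hypothesis; it does not threaten the trial's main conclusion on admission.

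**What to change.** Restate H2 along these lines: among all randomized Admission Phase participants, time from release to admission will be shorter in the Incentive group than in the Information group. Test it by log-rank or Cox regression, moved from Other Analyses to Hypothesis Testing, with those not admitted censored at a fixed, prespecified horizon. Report cumulative admission by day 14, which matches the voucher deadline. Keep days to admission among the admitted as a descriptive summary, labeled as a non-randomized comparison.

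State the limitation beside it: the test combines whether and when clients are admitted, so it overlaps with H1, and a positive result does not by itself show that anyone arrived sooner.

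The cost is small. Admission dates come from program records, time is already counted from release, and Cox regression is already in the plan. No new data or participants are needed. It is nevertheless a change in the question H2 asks and should be recorded as such.
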